### **1.11 Factors for Stratification**

Randomization will be stratified only by site. Site, baseline viral load, and baseline CD4 count will be used as covariates in the primary analysis.

### **1.12 Significance Testing**

With various analyses (primary and secondary) proposed in this protocol, there is a multiplicity of analyses to be performed, which leads to an increased probability that at least one of the comparisons could be "significant" by chance. The primary analysis simultaneously tests three separate hypotheses, and the overall experiment-wise type I error is controlled to be no more than 0.05 via a simple closed testing procedure.

For the secondary analyses we will not consider significance level adjustment. However, we will be conservative in the interpretation of these analyses, taking into account the degree of significance, and consistency across analyses. In addition, to guard against spurious significance results, we limited and pre-specified the secondary analyses.

### **1.13 Missing Data and Dropouts**

Missing data are a ubiquitous problem in substance use research, primarily due to dropping out and refusal. Missing data can lead to biased estimates and reduction of power, affecting the generalizability of the study. We will make every effort to minimize the amount of missing data and in the primary analyses we will include only participants with available data at 6 or 12 months, although study participants who have died will be considered a failure and not meeting virologic suppression. In all cases missingness patterns will be identified and analyses will be conducted to determine if there is differential non-death attrition by treatment arm, and if missingness is related to any of the covariates. In the case that covariates predict missingness, the data are called “Missing at Random,” (MAR) (Little & Rubin, 1987). GEE analyses are only appropriate if data are “Missing Completely at Random,” which means that no covariates predict the occurrence of missing data. Under the MAR assumption, the multiple imputations procedure can be used to fill in the data without artificially compressing the variance associated with the imputed data (Schafer, 1997). Therefore, if observed covariates predict the existence of missing data, multiple imputation will be used in a secondary analysis of the primary outcome to assess the effects of missingness on the reported results. If nonrandom missingness is of concern (Missing not at Random, MNAR), this problem will be addressed by applying pattern-mixture, propensity score or related models so that the effect of bias can be assessed in sensitivity analyses.

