### **1.6 Statistical Methods for Primary Analysis**

The primary hypothesis test will compare the proportions achieving HIV viral suppression at 12 months across the three study groups. Death from any cause will be considered equivalent to non-suppression for the purposes of calculating this proportion. (Differences in outcome when deaths are categorized with respect to likelihood of being HIV and/or drug use related will be explored in a secondary analysis.) All treatment comparisons will be performed under the Intent-to-Treat (ITT) criterion in the sense that participants will be analyzed in the arm to which they were randomized, regardless of subsequent events. However, participants who are lost to follow-up before 6 months will not contribute to the primary analysis. A Generalized Estimating

Equations (GEE) model will be employed (Zeger & Liang, 1986) with a binomial distribution and logit link as implemented in SAS. The GEE model will include both 6-month and 12-month HIV viral suppression status. However, the primary test of the hypothesis will be based on contrasts involving the 12-month proportions only. This model gains statistical power by pooling the error term across the two follow-up times and is closer to an ITT approach than would be the analysis of 12-month events only. It does not impute data that are missing at month 12 with the exception of death, which will be considered equivalent to non-suppression. Any potential correlation between patients within a site will be controlled by estimating a fixed effect for site in this model.

A simple closed-testing procedure (Westfall, Tobias, Rom, Wolfinger, & Hochberg, 1999) will be used to control family-wide type I error at 0.05 while still allowing all three pairwise comparisons between arms. Specifically, let  $P(123)$  be the (two-sided) p-value of the contrast testing equality among all three arms, while  $P(12)$ ,  $P(13)$ , and  $P(23)$  are the (two-sided) p-values for arms 1&2, 1&3, and 2&3, respectively. Then, let the adjusted p-value for the (1,2) comparison be

$$P^*(12) = \max[P(123), P(12)]$$

and similarly for the other pairwise comparisons. Tests of pairwise equality will be performed by comparing  $P^*(12)$ ,  $P^*(13)$ , and  $P^*(23)$  to the 0.05 level of significance.

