## 1.7 Rationale for Sample Size and Statistical Power

Power calculations were based on a simulation of several scenarios, with 5000 iterations per scenario. In each iteration, 266 virally unsuppressed participants were recruited to each of three treatment groups, after which death and dropout rates, and rates of suppression before and after 6 months, were imposed so as to result in proportions of simulated participants dead, lost, suppressed, and unsuppressed at both 6 and 12 months as indicated below. These rates characterized the scenario. (Note that the rates dictate the probabilities of joint occurrences of outcomes at 6 and 12 months, but it is possible for more than one set of rates to produce the same set of 6-month and 12-month margins.)

Once these data were simulated, they were subjected to a Generalized Estimating Equation (GEE) analysis in which dropouts were ignored and dead participants were combined with unsuppressed participants. More specifically, the GEE regressed state (suppressed versus unsuppressed or dead) on time (6 months, 12 months), treatment group (Patient Navigator = PN, Contingency Management + Patient Navigator = CM, Treatment as usual = TAU) site (1-10) and the time by treatment group interaction using a binomial link. The outcome of interest was the proportion suppressed (versus unsuppressed or dead) in each arm at 12 months, but the analysis incorporated 6-month data so that the 6-month/12-month correlation could in part offset loss to follow-up between 6 and 12 months. Contrasts were used to obtain p-values for the hypotheses CM=PN=TAU, CM=PN, CM=TAU, and PN=TAU with respect to the outcome of interest.

These p-values were combined together using the closed-testing methodology explained in Section 1.6. Note was taken of which of the pairwise hypotheses were rejected ( $\alpha = 0.05$ , two-tailed), and which accepted according to the Closed testing algorithm in each iteration. Finally, the power for the tests of the various hypotheses was estimated as the proportion of the 5000 iterations in which each hypothesis was rejected.

The scenarios were defined by the following parametric values, which varied from treatment group to treatment group:

- M6 = target suppressed proportion at 6 months (assuming no death or dropout)
- M12 = target suppressed proportion at 12 months (assuming no death or dropout)
- S = Probability that a participant will be suppressed at 12 months, given he was suppressed at 6 months

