- U = Probability that a participant will be unsuppressed at 12 months, given that he was unsuppressed at 6 months
- E = quarterly probability of death for a suppressed participant
- F = quarterly probability of death for an unsuppressed participant
- G = quarterly dropout probability for a suppressed participant
- H = quarterly dropout probability for an unsuppressed participant

Four scenarios (A-D) were investigated, with parametric values given by the table below:

Scenario	Group	M6	M12	S	U	E	F	G	H
A	TAU	0.18	0.16	0.95	0.99	0.02	0.05	0.04	0.04
A	PN	0.375	0.26	0.85	0.99	0.02	0.05	0.04	0.04
A	CM	0.55	0.4	0.85	0.98	0.02	0.05	0.04	0.04
B	TAU	0.175	0.16	0.98	0.99	0.015	0.03	0.03	0.03
B	PN	0.33	0.24	0.94	0.98	0.015	0.03	0.03	0.03
B	CM	0.49	0.44	0.96	0.98	0.015	0.03	0.03	0.03
C	TAU	0.175	0.16	0.98	0.99	0.02	0.05	0.04	0.04
C	PN	0.33	0.24	0.94	0.98	0.02	0.05	0.04	0.04
C	CM	0.49	0.44	0.96	0.98	0.02	0.05	0.04	0.04
D	TAU	0.18	0.16	0.95	0.99	0.015	0.03	0.03	0.03
D	PN	0.375	0.26	0.85	0.99	0.015	0.03	0.03	0.03
D	CM	0.55	0.4	0.85	0.98	0.015	0.03	0.03	0.03

The numerical values of the parameters selected in scenarios A-D were chosen to match prior experience of the investigators and data from the literature. Out of care HIV-infected individuals who are admitted to the hospital will have very low rates of viral suppression, in the range of 10-15%. From clinical discussions amongst the research team it was decided that a 10% to 12% increase (i.e., moving from 15% to 25% or 15% to 27%) is a minimally clinically meaningful change. We therefore aimed power determination at uncovering around a 12% pair-wise difference between intervention conditions. From an ongoing study of [name] and [name], a 12-15% death rate seemed to be likely in this cohort. Finally, since all participants are heavy drug and/or alcohol users it is appropriate to account for 10-15% attrition (in addition to the deaths) in these calculations even though, the research team has a history of achieving high rates of follow-up.

Power results are given in the following table, along with the parametric value of M12 and simulated resulting proportions of death, attrition, and suppression ignoring dropouts. Across each of the 4 scenarios, there is 87% power or greater to reject any of the 3 pair-wise comparisons under the assumptions set forth and a sample size of 266 study participants per treatment group.

Scenario	12-Month Statistics (percent)														

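### Section 1.13 guarantees no missing-data sensitivity analysis: imputation depends on a covariate screen that cannot establish MCAR, and the MNAR analysis has no stated criterion

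*SAP*

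**What the plan says.** **Primary analysis.** SAP section 1.6 fits a GEE to 6- and 12-month suppression and tests the 12-month contrasts. Deaths count as non-suppression. Section 1.13 admits anyone with data at either visit, while section 1.6 states that "participants who are lost to follow-up before 6 months will not contribute to the primary analysis".

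**Imputation.** In section 1.13, GEE is called appropriate only under MCAR, "which means that no covariates predict the occurrence of missing data". Attrition by arm and the relation of missingness to covariates are to be examined in all cases. Imputation is conditional on the result: "if observed covariates predict the existence of missing data, multiple imputation will be used in a secondary analysis of the primary outcome". The covariates are not listed and no threshold is given. The 6-month outcome is not named. Differential attrition by arm is examined but is not stated as a trigger.

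**MNAR.** If nonrandom missingness is thought to be a concern, "this problem will be addressed by applying pattern-mixture, propensity score or related models". No criterion is given and no one method is chosen.

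**Planning assumptions.** Section 1.7 says "it is appropriate to account for 10-15% attrition (in addition to the deaths) in these calculations". Every scenario gives suppressed and unsuppressed participants the same quarterly dropout probability (G = H).

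**The concern.** Followed as written, the plan allows the primary result to be reported with no missing-data sensitivity analysis. This would happen if no covariate reached whatever threshold is used and nobody declared a concern about MNAR.

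The screen cannot bear that weight, for three reasons.

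- MCAR requires missingness to be independent of the outcomes, observed and unobserved, as well as of covariates. A screen that finds no covariate predictor leaves dependence on suppression untested.
- Dependence on covariates already in the model (site, baseline viral load and CD4 indicators) is the least harmful kind for a GEE, yet it would trigger imputation. Dependence on unobserved suppression, the harmful kind, would not.
- Propensity-score methods work from observed data, so they do not by themselves address the MNAR case for which they are listed.

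At stake is the credibility of the 12-month contrasts. Section 1.7 expects 10-15% attrition beyond deaths in a heavily drug- or alcohol-using cohort. Suppression could plausibly affect who is lost, and navigation could change retention by arm.

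**Working it through.** **1. Reproducing the plan's own figures.** Section 1.7 states that "266 virally unsuppressed participants were recruited to each of three treatment groups" and that "there is 87% power or greater to reject any of the 3 pair-wise comparisons". Scenarios A-D were re-simulated from M6, S, U and E-H (1,500 iterations; GEE with exchangeable correlation; deaths as failures; closed testing at 0.05). Site was left out, everyone was assumed unsuppressed in the first quarter, and hazards in months 6-12 followed 6-month status.

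| Scenario | Stated power (TAU-PN / PN-CM / TAU-CM) | Re-simulated |
|---|---|---|
| A | 93 / 87 / 100 | 93.3 / 88.5 / 100 |
| B | 94 / 92 / 100 | 94.3 / 92.8 / 100 |
| C | 93 / 89 / 100 | 91.5 / 89.3 / 100 |
| D | 94 / 89 / 100 | 95.5 / 90.9 / 100 |

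All agree within 2 points, so the plan's parameters are a sound base for the checks below.

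**2. How many are lost, and when.** Scenario A, CM arm: M6 = 0.55, S = 0.85, U = 0.98, E = 0.02, F = 0.05, G = H = 0.04. Death is applied before dropout in each quarter.

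- Quarter 1: dead 0.05; lost 0.95 × 0.04 = 0.038; remaining 0.912.
- Quarter 2, suppressed: 0.912 × 0.55 = 0.5016; lost 0.5016 × 0.98 × 0.04 = 0.0197; remaining 0.4719.
- Quarter 2, unsuppressed: 0.912 × 0.45 = 0.4104; lost 0.4104 × 0.95 × 0.04 = 0.0156; remaining 0.3743.
- Lost before 6 months: 0.038 + 0.0197 + 0.0156 = **0.073**, or about 19 of 266 per arm.
- Months 6-12: suppressed 0.4719 × (0.98 × 0.96)² = 0.4177; unsuppressed 0.3743 × (0.95 × 0.96)² = 0.3113.
- Suppressed at 12 months: 0.4177 × 0.85 + 0.3113 × 0.02 = 0.3613. Total lost: 0.136.

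Scenario B's rates give 5.7% lost before 6 months and about 10.7% in total.

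**3. Bound: everyone lost is unsuppressed (Scenario A).** Observed proportion = suppressed ÷ (1 − lost). With missing counted as failure, the proportion is the suppressed share itself.

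| | TAU | PN | CM | PN-TAU | CM-PN |
|---|---|---|---|---|---|
| Lost | 13.4% | 13.5% | 13.6% | | |
| Observed | 15.7% | 28.5% | 41.8% | 12.8 | 13.3 |
| Missing = failure | 13.6% | 24.6% | 36.1% | 11.1 | 11.5 |

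The table's whole percentages give nearly the same answer: 29 × 0.86 = 24.9 and 42 × 0.86 = 36.1, so CM-PN goes from 13.0 to 11.2. If attrition were 10% in PN and 18% in CM (an assumption), 29 × 0.90 = 26.1 and 42 × 0.82 = 34.4, a difference of 8.3 points.

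**4. Dropout driven by observed 6-month status.** Dropout in months 6-12 was made to depend on 6-month status (400,000 simulated per arm). The quarterly rates are assumptions.

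| Scenario A, CM arm | True | 12-month completers | Planned GEE |
|---|---|---|---|
| 2% suppressed, 8% unsuppressed | 42.5% | 43.9% | 42.0% |
| 1% suppressed, 10% unsuppressed | 42.5% | 45.0% | 41.9% |

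In every Scenario A and B case run, the GEE was within about 0.6 points of the truth. Completers alone were off by up to about 3.5 points. At 2%/8%, the GEE's CM-PN difference is 42.0 − 28.6 = 13.4, against a true 42.5 − 28.9 = 13.6.

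**5. Dropout before 6 months, status never observed.** Assume quarterly rates in CM of 1% (suppressed) and 8% (unsuppressed), and in PN of 2% and 4.5%, confined to the first 6 months. The model in step 2 then gives CM-PN of 43.5 − 29.3 = 14.2, against a no-dropout 42.5 − 29.0 = 13.5. The overstatement is about 0.7 points. Including 6-month status cannot repair this, because it was never measured in these participants.

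**6. How often the screen stays silent.** If dropout is unrelated to every screened covariate, the chance that none reaches p < 0.05 is 0.95^k: 86% for k = 3 and 63% for k = 9, assuming independent tests at 0.05. Imputation would then not run, however strongly dropout depended on suppression.

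**The case against.** The plan is better than a quick reading suggests, and much of the defence stands.

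- A reader might infer that the primary analysis is complete-case. It is not: the GEE uses everyone with 6- or 12-month data and counts deaths as failures. Section 1.7 says the 6-month data are there partly to offset later loss.
- A reader might infer that leaving the 6-month outcome unnamed in the screen is the main weakness. It is not: that outcome is already a response in the model, and step 4 shows little bias from it. Because the covariates are not listed, the screen cannot be said to exclude it either.
- A reader might infer that no MNAR method is planned. Pattern-mixture modelling is named, and it is a standard one.
- Keeping the GEE as primary whatever the screen shows is sound pre-specification. Switching the primary model on a data-dependent screen would be worse.
- Section 1.6 qualifies its use of ITT and discloses the exclusion of early losses. G = H is a power assumption and is not itself a fault in the missing-data plan.
- With equal attrition, the worst case in step 3 leaves differences of 11.1 and 11.5 points, still within the 10-12 points that section 1.7 treats as minimally meaningful.

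None of this supplies an unconditional check, a criterion for MNAR concern, or a valid reason to cancel imputation after a null screen.

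**Conclusion.** The point holds as a fault in the stated rule. Both sensitivity routes in section 1.13 are conditional: one on a screen built on an incorrect definition of MCAR, the other on an undefined concern. The exposure lies in the roughly 6-7% lost before 6 months and in dropout that depends on unobserved suppression.

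Its size is moderate. With equal attrition, the Scenario A bound takes CM-PN from 13.3 to about 11.5 points. With assumed attrition of 10% in PN and 18% in CM, the difference is 8.3 points, below the range that section 1.7 calls meaningful. These bounds rest on the plan's own rates, on everyone starting unsuppressed, and on all lost participants being failures. They show what could happen and do not predict bias.

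The documents do not support the stronger inference that the primary test, the power or the sample size is wrong. The stated power reproduces, and none of these is affected. Nor would MAR imputation alone settle the matter, since it does not test dependence on unobserved status. A separate MNAR analysis is needed.

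**What to change.** Keep the GEE as the primary analysis and amend section 1.13 before unblinding, so that two analyses are always reported:

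1. Multiple imputation of 6- and 12-month status, done by arm, using 6-month status, site, baseline viral load, CD4 and drug-use type, with deaths fixed as failures.
2. One named MNAR analysis covering all randomised participants: missing counted as not suppressed, a delta-adjusted tipping-point analysis, or both.

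In the same section, correct the MCAR definition to include independence from observed and unobserved outcomes. Remove propensity score from the MNAR list. Keep the missingness screen as description only, and add 6-month status to it for those lost later.

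The cost is SAP wording and a few extra analysis runs. No new data are needed.

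### Multiple imputation of the primary outcome depends on a covariate test built on a wrong definition of MCAR, and the MNAR analysis on an undefined condition, so no missing-outcome sensitivity analysis is guaranteed

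*SAP*

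**What the plan says.** The primary analysis (SAP 1.6) is a logit GEE on 6- and 12-month suppression, tested on the 12-month contrasts. On missing data:

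- Early losses are excluded: "participants who are lost to follow-up before 6 months will not contribute to the primary analysis".
- On 12-month values: "It does not impute data that are missing at month 12 with the exception of death". Section 1.13 agrees: "in the primary analyses we will include only participants with available data at 6 or 12 months".
- Section 1.13 explains MCAR with the words "which means that no covariates predict the occurrence of missing data". It introduces MAR with "In the case that covariates predict missingness, the data are called", followed by that label.
- From this it derives the rule for imputation: "if observed covariates predict the existence of missing data, multiple imputation will be used in a secondary analysis of the primary outcome".
- One check is unconditional: "In all cases missingness patterns will be identified and analyses will be conducted to determine if there is differential non-death attrition by treatment arm". The same sentence adds the relation of missingness to covariates. No consequence is attached to the by-arm result.
- For non-random loss: "If nonrandom missingness is of concern (Missing not at Random, MNAR), this problem will be addressed by applying pattern-mixture, propensity score or related models". These would be sensitivity analyses.

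**The concern.** The definitions are wrong, and they decide what is run. MCAR means that missingness is unrelated to covariates and to the outcome, observed or not. MAR means that, given the observed data, missingness does not depend on the unobserved values. Neither can be read off a test of covariates against missingness. If living patients are lost because they have left care and are unsuppressed, the covariate test may be null, and the SAP would then treat the data as MCAR.

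Section 1.13 names treatment arm separately from the covariates, so unequal attrition by arm does not itself start the imputation. The MNAR step has no threshold and leaves the method open among several. The unconditional sensitivity analysis in 1.6.1 adds covariates to the model and does nothing about missing outcomes.

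At stake is the robustness of the trial's single primary outcome. Both gates can stay closed, and both would be settled after the data are seen.

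**Working it through.** **1. The plan's own power figures.** Inputs from SAP 1.7: 266 per arm and the scenario table (M6, S, U, E, F, G, H). Method: draw 6-month status from M6 and 12-month status from S and U; apply death and dropout quarterly; count deaths as unsuppressed; fit a logit GEE with exchangeable correlation and robust standard errors; test the 12-month contrasts with P*(ij) = max[P(123), P(ij)]. There were 1,500 runs per scenario. Site and baseline covariates were left out.

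| Scenario | SAP power: TAU-PN / PN-CM / TAU-CM | Simulated |
|---|---|---|
| A | 93 / 87 / 100 | 94.1 / 88.9 / 100 |
| B | 94 / 92 / 100 | 94.9 / 93.3 / 100 |
| C | 93 / 89 / 100 | 93.7 / 90.9 / 100 |
| D | 94 / 89 / 100 | 95.5 / 89.5 / 100 |

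All are within 2 points, so the SAP's figures reproduce.

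**2. What those figures assume.** Quarterly dropout is the same for suppressed (G) and unsuppressed (H) patients in all 12 rows: 0.04 in A and C, 0.03 in B and D. Outcome-related loss was never examined.

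**3. Unequal retention, all lost patients unsuppressed.** The retention values are my assumptions. Let p be the true suppressed share, equal in all arms, and r the retention in an arm. If no lost patient is suppressed or has a 6-month value, the observed share is p/r. I took p = 16% and 29%, the realized values for TAU and PN in scenario A.

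- p = 29%, r = 0.90 vs 0.80: observed 32.2% vs 36.2%. SE = √[0.322×0.678/(266×0.90) + 0.3625×0.6375/(266×0.80)] = 0.0447. Shift = 0.0403/0.0447 = 0.90 SE. Unadjusted two-sided rejection is 14.7%.
- p = 16%, same retention: 17.8% vs 20.0%, shift 0.60 SE, rejection 9.2%.
- r = 0.88 vs 0.82: 6.5% (p = 16%) and 8.4% (p = 29%).

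These rates ignore the closed test. Simulating with the SAP's rule gives:

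| Retention of the pair | Third arm | Error for that pair | Family-wise error |
|---|---|---|---|
| 90% vs 80% | 80, 85 or 90% | about 5-9% | about 8-14% |
| 88% vs 82% | 85% | about 3.3-4.5% | about 6-7% |

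**4. Would the by-arm attrition check notice?** A 5% test is assumed, since the SAP gives no level.

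- 90% vs 80%: z = 0.10/√[(0.90×0.10 + 0.80×0.20)/266] = 0.10/0.0307 = 3.26. Detection is about 90% by this formula and 91% by simulation.
- 88% vs 82%: z = 0.06/√[(0.88×0.12 + 0.82×0.18)/266] = 0.06/0.0309 = 1.94. Detection is about 49%.

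**5. Similar attrition, different kinds of patient lost.** Scenario A's PN parameters were used in all three arms, so there is no true difference. The G and H values that depart from the SAP's are assumptions.

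| Dropout (G/H) | 12-month suppression | Family-wise error |
|---|---|---|
| 0.04/0.04 in all arms | 29.7% | 4.5% |
| 0/0.06 in all arms | about 32.6% (29.9% without dropout) | 4.8% |
| 0/0.06 in one arm, 0.04/0.04 in the others | 32.6% vs 29.7% | 10.9% |
| 0/0.06, 0.04/0.04 and 0.06/0.03 | 32.5%, 29.6%, 28.4% | 13.2% |

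The Monte Carlo standard error at 10.9% is √(0.109×0.891/1500) = 0.8 points. In the third row attrition is 12.6% vs 13.7%, so z = 0.011/√[(0.126×0.874 + 0.137×0.863)/266] = 0.011/0.0293 = 0.38. The by-arm check would almost never flag it. Power can also suffer: in scenario A with TAU alone at G = 0, H = 0.05, TAU-PN power falls from 94.1% to 86.7%.

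**6. Loss after 6 months that depends only on 6-month status.** In a large sample the GEE gave 0.328 against a true 0.330, while the observed 12-month cases alone gave 0.354. The 6-month data largely handle this. The exposure is loss before 6 months and loss tied to the unseen 12-month status.

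**The case against.** A reader might infer that no check is run at all. The SAP does not support that: patterns and by-arm attrition are examined in every case, and an MNAR analysis may be run. At 90% vs 80% retention, the chance of falsely rejecting that pair with no attrition flag is only 0.5-0.9%. This stands. But a flag obliges nobody to do anything, it comes only about half the time at 88% vs 82%, and it is blind to the case in step 5 where attrition totals are similar.

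A reader might also quote the unadjusted 9-15% as the type I error for a pair. The closed test brings that to about 5-9%, and at 88% vs 82% to below 5%. Only the family-wise rate stays above 5%.

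Nor should one example stand for the trial. Take observed rates of 29% vs 42%, with retention of 90% and 80% respectively. Counting missing as failure gives 0.29×0.90 = 26.1% vs 0.42×0.80 = 33.6%, and z falls from 2.9 to 1.9. Reverse the retention and the gap widens to 37.8% − 23.2% = 14.6 points. The direction is unknown.

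The covariate trigger is not useless. Age, race and ethnicity, gender and drug type are outside the primary GEE; if they predict both loss and suppression, imputation using them helps. With several covariates the trigger may well fire. Finally, imputation under MAR does not repair MNAR loss, so making it unconditional is not enough on its own.

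**Conclusion.** Section 1.13 is wrong as written. It misdefines MCAR and MAR and makes the imputation decision follow from that error; the MNAR analysis has no criterion and no chosen method. The supported conclusion is that no missing-outcome sensitivity analysis of the primary result is guaranteed. It does not follow that none will be done or that the primary result will be biased.

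The size depends on assumed loss patterns. If every lost patient is unsuppressed with no 6-month value, family-wise error is about 8-14% at 90% vs 80% retention and about 6-7% at 88% vs 82%. It is about 11% when outcome-related loss is confined to one arm and attrition totals are similar. If such loss is the same in all arms, suppression is overstated by about 3 points but family-wise error stays near 5%. The first two figures are upper-range because they take every lost patient to be unsuppressed.

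**What to change.** In SAP 1.13, correct the MCAR and MAR sentences, and remove both the covariate-test trigger and the undefined condition on the MNAR step. State that, whatever the missingness tests show, two analyses covering all randomized participants are reported beside the unchanged primary GEE:

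1. Multiple imputation by arm, using site, baseline viral load, baseline CD4, the covariates listed in 1.6.1 and 6-month status.
2. One named MNAR analysis: a delta-adjusted tipping point on that imputation, with shifts allowed to differ by arm.

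Counting missing as non-suppressed may be shown as one extreme of (2), with a caution. Under purely random loss at 90% vs 80% and no effect, it compares 0.16×0.90 = 14.4% with 0.16×0.80 = 12.8% (or 26.1% with 23.2% at p = 29%), and its own unadjusted pairwise error is about 8-12%.

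The cost is a wording change and a few extra analyses to run and report.
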